#### **5.4.2** Adverse Events of Special Interest

Adverse events of special interest (AESI) include hepatic disorders (including changes in hepatic aminotransferases), musculoskeletal events (AE and CK evaluation), new onset diabetes/hyperglycemia, renal events, metabolic acidosis and/or hypoglycemia, and

Confidential Page 14 of 18

neurocognitive/neurologic events. These events will be pulled out of the AE databases by SOC and PT, and will be identified as safety monitoring endpoints.

- Hepatic safety will be assessed via liver-associated enzymes (eg, ALT, AST) and total bilirubin.
- Musculoskeletal safety will be assessed via AEs involving muscle related symptoms. Changes in creatine kinase (CK) values will also be summarized.
- New onset diabetes/hyperglycemia will be assessed via AEs and monitoring of glucose.
- Renal safety will be assessed via eGFR measurements, changes in serum creatinine and blood urea nitrogen values, as well as CK values.
- Neurocognitive events will be assessed by routine monitoring of PE findings and AEs.
- Hypoglycemia will be assessed by routine clinical laboratories and AEs and summarized based on AE evaluations
- Metabolic acidosis occurrences will be monitored by routine laboratories and summarized based on AE evaluations.

AESI will be presented in a listing and summarized by SOC, PT and treatment group. Muscle-related TEAEs will be summarized by SOC, PT, and baseline eGFR category.

### 5.4.3 Laboratory Evaluations

Continuous laboratory parameters (serum chemistry, hematology), urinalysis, urinalysis [microscopic]) listed in Table 4; and glucose will be summarized using descriptive statistics for the observed value and the change from baseline for all post-baseline study visits. Missing values for any of the laboratory evaluations will not be imputed; that is, only observed case data will be used. Baseline is defined as the last value prior to the first dose of study medication. Categorical urinalysis data will be provided in the listing.

Confidential Page 15 of 18

**Table 4:** Clinical Laboratory Parameters (Safety)

### Hematology

- Hematocrit (Hct)
- Hemoglobin (Hgb)
- Mean corpuscular hemoglobin (MCH)
- Mean corpuscular hemoglobin concentration (MCHC)
- Mean corpuscular volume (MCV)
- Platelet count
- Red blood (RBC) cell count
- White blood (WBC) cell count with differential (absolute and %)

#### Urinalysis (Dipstick)

- Clarity
- Bilirubin
- Color
- Glucose
- Ketones
- Leukocyte esterase
- Nitrate
- Occult blood
- pH
- Protein
- Specific gravity
- Urobilinogen

## Urinalysis (Microscopic)-only if urine

# dipstick abnormal

- Bacteria
- Casts
- Crystals
- Epithelial cells
- Red blood cell (RBC)
- WBC

### Blood Chemistry (serum, fasting)

- Albumin (Alb)
- Alkaline phosphatase (Alk-P)
- Alanine aminotransferase (ALT; SGPT)
- Aspartate aminotransferase (AST; SGOT)
- Blood urea nitrogen (BUN)
- Calcium (Ca)
- Carbon dioxide (CO2)
- Chloride (Cl)
- Creatinine
- Creatine kinase (CK)
- Glucose
- Lactate dehydrogenase (LDH)
- Phosphorus
- Potassium (K)
- Sodium (Na)
- Total and direct bilirubin (TB)
- Total protein
- Uric acid

Coagulation (In all patients at screening, then only in patients receiving anticoagulant therapy that in the investigator's judgment require monitoring at Visit T1 and 3 to 5 days post Visit T1)

- Prothrombin time (PT)
- International normalized ration (INR)

The number and percentage of patients with laboratory abnormalities (i.e., laboratory values outside the stated laboratory normal range) will be summarized at each time point (i.e., including baseline and post-baseline time points) for each laboratory parameter. The determination of laboratory abnormalities will take into account any unscheduled laboratory assessments. Additional lab-related summaries will be provided as follows for hepatic safety, musculoskeletal safety, diabetes and glycemia, and renal safety.

Confidential Page 16 of 18

### **5.4.4** Physical Examinations (PEs)

Listings of PE data will include only those records where the body system at the baseline PE was normal, but the body system at a post-baseline PE was marked as 'Change from previous exam, clinically significant.' Only changes from baseline physical examination findings that meet the definition of an AE will be recorded on the AE page of the eCRF and will be summarized with other AEs.

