13. ADVERSE AND SERIOUS ADVERSE EVENTS

13.1. Adverse Events

13.1.1. Definition of Adverse Events

An AE is defined as any untoward medical occurrence in a clinical investigation patient administered a pharmaceutical product, including control, and which does not necessarily have a causal relationship with treatment. The investigator is responsible for ensuring that any AEs observed by the investigator or reported by the patient are recorded in the patient's medical record.

An AE can be:

- Any unfavorable and unintended sign/symptom including an abnormal laboratory finding or disease temporally associated with the use of a medicinal product, whether or not considered related to the medicinal product
- Any new disease or exacerbation of an existing disease
- Laboratory abnormality or diagnostic test abnormalities (eg, electrocardiogram [ECG] or X-ray) should be reported as an AE if one of the following occurs:
 - Treatment required due to the abnormality
 - Discontinuation of IMP
 - Per Investigator judgement
- TEAEs are defined as AEs that begin or worsen after the first dose of IMP administration as defined in the statistical analysis plan (SAP)

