13.1.3. Reporting for Adverse Events

All AEs occurring during the course of the study (starting from signing informed consent through 30 days after study completion/discontinuation) will be collected on the AE eCRF. Patients should be instructed to report any AE that they experience to the investigator. Investigators should make an assessment for AEs at each visit and record the event on the appropriate AE eCRF.

Wherever possible, a specific disease or syndrome rather than individual associated signs and symptoms should be identified by the investigator and recorded on the eCRF. However, if an observed or reported sign or symptom is not considered a component of a specific disease or syndrome by the investigator, it should be recorded as a separate AE on the eCRF. Additionally, the condition that led to a medical or surgical procedure should be recorded as an AE, not the procedure.

Any medical condition already present at screening or baseline should not be reported as an AE unless the medical condition or signs or symptoms present at baseline worsens in severity or seriousness at any time during the study. In this case, it should be reported as an AE.

It is the responsibility of the investigator to assess the clinical significance of all abnormal values as defined by the list of reference ranges from the local laboratory. In some cases, significant changes in lab values within the normal range will require similar judgment.

An abnormal laboratory value that is not already associated with an AE is to be recorded as an AE only if any one of the following criteria is met:

- an action on the study drug is made as a result of the abnormality
- intervention for management of the abnormality is required
- at the discretion of the investigator should the abnormality be deemed clinically significant

Significant abnormal laboratory values occurring during the clinical study will be followed until repeat tests return to normal, stabilize, or are no longer clinically significant. Any abnormal test that is determined to be an error does not require reporting as an AE.

Each AE is to be evaluated for duration, severity, seriousness, and causal relationship to the IMP. For each AE, the following information will be recorded:

- Description of the event (eg. headache)
- Date of onset
- Date of resolution (or that the event is continuing)
- Action taken as a result of the event
- Seriousness of the event
- Severity of the event
- Outcome of the event

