#### 3.2.3 Safety Endpoints

- Patient incidence of adverse events
- Clinical safety laboratory (including hematology, blood chemistry, and urinalysis) results
- Vital signs and physical examination (PE) findings

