# 5.4 Safety Endpoints and Analyses

For all safety endpoints, the safety population (SP) will be used. Descriptive summary will be provided for safety endpoints.

The summarization of AEs will include only TEAEs (defined as AEs that begin or worsen after the first dose of double-blind IMP until 30 days after last dose of IMP). All TEAEs, SAEs, AEs leading to withdrawal of IMP, fatal AEs and AEs of special interest will be summarized by MedDRA SOC and preferred term in descending order of frequency by treatment group.

Clinical safety laboratories, including hematology, blood chemistry, glucose, and urinalysis; PE findings; vital signs; and weight will be summarized by the value and by change or percent change from baseline in the value (where appropriate) at each postbaseline time point.

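### The physical-examination listing in SAP 5.4.4 omits clinically significant changes in body systems that were already abnormal at baseline

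*SAP*

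**What the plan says.** SAP 3.2.3 names the examination as a safety endpoint: "Vital signs and physical examination (PE) findings". SAP 5.4 promises that "PE findings; vital signs; and weight will be summarized by the value and by change or percent change from baseline", where appropriate, at each post-baseline time point. Protocol 14.7 says the same. Neither sentence filters on baseline status.

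SAP 5.4.4, the section devoted to physical examinations, sets two joint conditions for the listing. The first is "Listings of PE data will include only those records where the body system at the baseline PE was normal". The second is "but the body system at a post-baseline PE was marked as 'Change from previous exam, clinically significant". The section then turns to AEs: "Only changes from baseline physical examination findings that meet the definition of an AE will be recorded on the AE page of the eCRF". It describes no table of PE findings by value or by change.

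SAP 5.4.2 names the examination as a source for one event of special interest: "Neurocognitive events will be assessed by routine monitoring of PE findings and AEs".

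**The concern.** A safety listing should show the changes an examiner judged to matter. This one admits such a change only if the body system started out normal. A patient with an abnormal musculoskeletal or neurologic examination before dosing could be marked at Week 6 as having a clinically significant change in that system and still not be listed. Because the filter works by body system, a new finding unrelated to the old one is left out as well.

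What is at stake is a cross-check. The PE listing is the one specified output that shows the examiner's mark independently of the decision to record an AE. A significant change without a matching AE would be visible for a system normal at baseline and hidden for one that was abnormal. Muscle and neurocognitive events are of special interest in this trial, and Protocol 12.1.4 includes musculoskeletal and neurologic examinations, so the affected systems are not remote ones.

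**Working it through.** No arithmetic applies: the point concerns a listing rule, and the plan gives no figure to reproduce. The check applies the rule to each case and compares it with the rest of the plan.

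**The rule in SAP 5.4.4**

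| Baseline status of the body system | Post-baseline examination | Listed? |
|---|---|---|
| Normal | Marked as clinically significant change | Yes |
| Abnormal | Marked: old finding worse | No |
| Abnormal | Marked: new, unrelated finding | No |
| Either | Not so marked | No |

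The second and third rows are the gap.

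**Other routes for those two rows**

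1. *AE output.* The AE sentence in SAP 5.4.4 has no baseline-normal condition. A change that meets the AE definition goes on the AE page. SAP 5.4 counts AEs that begin or worsen after the first dose as treatment-emergent, and SAP 5.4.1 lists all AEs. This route is open, but it depends on the change being judged to meet the AE definition.
2. *PE summary.* SAP 5.4 promises one without the filter. SAP 5.4.4 does not say what it contains or whether it will be made.

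**Other safety domains.** SAP 5.4.3 counts laboratory abnormalities at every time point, including baseline. SAP 5.4.5 lists vital signs for each patient. Of the safety domains, only the PE listing is filtered on a normal baseline, and the SAP gives no reason.

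**The baseline itself.** The listing depends on which examination is the baseline. Protocol 10.5.3 and the Protocol Appendix 1 schedule place it at T1 (Day 1). The SAP Appendix 1 schedule places it at S2 (Day -10 to -7) and shows none at T1. The baseline definitions in SAP 5.2.2 cover lipids, hs-CRP, other laboratory evaluations and vital signs, but do not mention the examination.

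**Size.** Records omitted from the listing for a given system = patients examined × share abnormal at baseline × share of those later marked as significantly changed. Changes missing from both the listing and the AE output = that product × share not recorded as AEs. The documents give none of the three shares. They do bound the listing: about 60 patients with one scheduled post-baseline examination each (Week 6 or early termination) makes about 60 × 1 = 60 scheduled examinations.

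**The case against.** The strongest reply is that the AE rules already cover this. Protocol 13.1.1 includes in the AE definition "Any new disease or exacerbation of an existing disease". Protocol 13.1.3 says a condition present at baseline is not an AE "unless the medical condition or signs or symptoms present at baseline worsens in severity or seriousness at any time during the study", in which case it should be reported as one. Significant findings before dosing go on the medical history page, which SAP 5.4.4 does not restrict and SAP 5.2.6 summarizes and lists by patient. To be missing from both the listing and the AE output, a change must be marked clinically significant and yet not be recorded as an AE. Limiting a listing to new abnormalities and leaving worsening to AE reporting is a coherent design.

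Most of that stands, and it makes the consequence small. It does not restore the cross-check, because the residual case is the very mismatch a PE listing can reveal.

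A reader might infer more than the text supports:

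- *That such changes vanish from all PE output.* The filter governs listings only; SAP 5.4 promises a separate, unfiltered summary, although it is undefined.
- *That the trial cannot see worsening in these patients.* AE reporting remains open to them. SAP 5.4.2 assesses muscle safety through AEs and CK, and neurocognitive safety through AEs as well as the examination. It draws events of special interest from the AE database, not from the PE listing.
- *That the share of patients abnormal at baseline measures the loss.* That share counts patients to whom the filter could apply, not findings lost, and the documents do not give it.

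**Conclusion.** The point holds as a stated exclusion in one listing, at low severity. A clinically significant change in a system abnormal at baseline is omitted from the only PE output that the SAP specifies in detail. It appears elsewhere only through AE recording or through the undefined summary in SAP 5.4.

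The effect is limited to descriptive safety reporting. No efficacy estimate, test, analysis population or error rate changes. No count of affected records can be given. The conclusion rests on reading 5.4.4 literally and on the change mark being collected for every body system whatever its baseline status, as the wording of 5.4.4 implies but does not state.

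**What to change.** In SAP 5.4.4:

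1. Delete the baseline-normal condition. List every post-baseline record marked as a clinically significant change, with the baseline status of that body system as a column.
2. Add a count of such changes by arm and body system, and state that this is the PE summary meant in 5.4, so that the two sections agree.

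Separately, reconcile the baseline examination visit between the protocol (T1) and the SAP schedule (S2), and say in the SAP which examination serves as the baseline.

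The cost is one condition removed, one small table and a few more listing rows. With about 60 scheduled post-baseline examinations the listing stays short, and no new data are needed if the mark is collected as assumed above.

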#### 5.4.5 Vital Signs

Actual values and changes from baseline in vital signs (heart rate, systolic blood pressure, diastolic blood pressure, weight, height [baseline only], and BMI) will be summarized using descriptive statistics by treatment group and post-baseline time point on the observed values. Baseline is defined as the last value prior to the first dose of study medication, except baseline of blood pressure is defined as mean of 2 measures at same visit.

Vital signs data will be listed for each patient, with increases from baseline of >15 mmHg in systolic or diastolic blood pressure flagged.

For vital signs, observed values and changes from baseline will be summarized for all post-baseline study visits.

# 7 Appendices

**Appendix 1: Schedule of Events (Patient Visit Schedule)** 

	Scr	een	Treatment			
Visit	S1	S2 	T1	T2	Т3	
Week	-6	-1	0	3	6/EOS/ET 	
Procedure	Day -42 to -37	Day -10 to -7	Day 1	Day 22 ± 3	Day 43 ± 3	
Informed Consent	X	-				
Enrollment Criteria	X	X	X			
Demographics	X					
Medical History	X					
Concomitant\Prohibite	X	X	X	X	X	
d Medications						
Adverse Event		X	X	X	X	
Recording						
Physical Exam		X			X	
Weight 	X		X		X	
Height/BMI	X					
Vital Signs 	X	X	X	X	X	
Serology 		X				
Serum Pregnancy	X					
and/or FSH 						
Urine Pregnancy 			X			
TSH	X					
Clinical Safety Labs 	X		X	X	X	
Basic Fasting Lipid 	X	X	X	X	X	
Special Fasting Lipids			X		X	
and Other Biomarkers 						
Dietary and Lifestyle	X	X	X	X		
Counselling						
Randomization			X			
Double-blind IMP			X	X		
Dispensing						
IMP Drug Return				X	X	

BMI = body mass index; FSH = follicle-stimulating hormone, TSH = thyroid-stimulating hormone, EOS = End of Study, ET = Early Termination.

Confidential Page 18 of 18

 An optional visit approximately 1 week later MAY be completed if patient fails to meet a lipid entry criterion. If this optional visit is completed, the mean of the LDL-C values, or TG values, will be used to determine eligibility.

 All procedures will be completed at end of study or early termination.

 Body weight will be measured in the morning while fasting, using consistent scales, after voiding, and without shoes and outerwear (eg, coats).

 Vital signs will include SBP, DBP, and heart rate, and will be collected prior to any blood sample collection. Patient will rest for 5 minutes prior to assessments.

 Serology for Hep B antigen, Hep C antibody.

 FSH completed in appropriate postmenopausal women only; pregnancy test completed in non-postmenopausal women only.

 Clinical safety labs include hematology, blood chemistry, and urinalysis. Coagulation panel ONLY in patients receiving anticoagulants measured only at T1 and repeat 3-5 days after starting IMP.

 Basic fasting lipids include total cholesterol, calculated LDL-C, HDL-C, non-HDL-C, and triglycerides.

 Includes ApoB and hs-CRP
